- b. **How data will be coded, recorded, and stored to protect confidentiality:** All samples and data generated from the research study will be labeled and/or recorded with a unique code number and no other identifier. The information that will allow the unique code number to be linked to the volunteer's name will be stored as a password-protected computer file. Samples will be stored until all analyses are complete. If blood samples collected during the course of this research study are sent outside the HNRCA for analysis, they will be labeled in a manner that contains no information that can make it possible to trace the sample back to the volunteer as an individual. At the conclusion of the study, the information file that would allow linking of the volunteer's identification information with the sample labels will be destroyed. Therefore, after the research study is completed, the identity of subjects will not be traceable to the data and samples stored. Study data will be collected and managed using REDCap (Research Electronic Data Capture). REDCap is a secure, HIPAA and 21 CFR 11 compliant web-based application designed to support data capture for research studies, providing user-friendly web-based case report forms, real-time data entry validation (e.g. data types and range checks), complete audit history, restricted access to PHI and a de-identified export mechanism to common statistical packages (SPSS, SAS, Stata, R/S-Plus). REDCap is hosted by the Tufts University Clinical and Translational Science Institute (CTSI) and is made freely available to the Tufts CTSI research community. Vanderbilt University was responsible for leading the development of the system and along with a consortium of over 1600 member institutions provides a significant amount of online training material to support researchers developing studies using this platform. Tufts CTSI compliments this resource with a series of classes to further support, train and empower the researcher in their endeavors. In addition, the Biostatistics and Data Management Core Unit of the Jean Mayer USDA Human Nutrition Research Center on Aging provides planning assistance and support for development of REDCap data collection projects thorough study-specific data dictionaries defined by members of the research team. The Tufts CTSI - REDCap deployment employs a MySQL 5.x database and a Microsoft IIS web server located within Tufts Medical centers' DMZ and is accessible via a secure SSL connection.

Confidentiality of Employee-subjects: The identity of the employee-subjects, their medical records, and the data relating to this research will be kept confidential, except as required by law. Under no circumstances will the data related to this

research, or their medical records be linked to the employee ID number. Upon entry into the research study the employee-subject will be assigned a unique code number. For storage, blood samples will be identified with this unique code number (not related to medical record number, or employee ID number), date, laboratory generated login number and sample description (i.e. plasma, serum). All samples and data generated from the research study will be labeled and/or recorded with that number and no other identifier. Therefore, after the research study is completed, the identity of subjects will not be traceable to the data and samples stored.

Record Retention Plan: Volunteers' records will be filed in the Metabolic Research Unit's Medical Records File Room located on the 11th Floor of the Human Nutrition Research Center. Research records will be stored in a locked file cabinet in the Principal Investigator's office. Digital data records, in the form of excel spreadsheets, will be stored in the Principal Investigators' password-protected computer. Research records, including volunteer records, will be retained for a period of 7 years after completion of the study, in agreement with Tufts MC / TUHS IRB record retention policies and requirements.

- c. **Parties who will have access to the data, including the key to the identity code:** [name] (Principal Investigator) will have access to the key to identity code. [name] will have access to the de-identified data. Laboratory personnel responsible for analyzing the samples will have access only to the de-identified data. The study statistician (to be identified) will have access only to the de-identified data.
- d. **Parties who will have access to research records:** PI and co-investigators will have access to the research records.

11. **Alternatives:** The volunteer can choose not to participate in this research study. S/he is free to withdraw from this study at any time for any reason.

- H. **Outcome:** Determine the common and distinct effects of EPA versus DHA on inflammation and lipid metabolism. This information will lead to targeted and personalized use of these fatty acids.

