- alcohol consumption > 7 drinks/week
- uncontrolled thyroid dysfunction
- insulin-dependent type 2 diabetes mellitus
- kidney or liver disease
- smoking
- alterations in coagulation (prolonged partial thromboplastin time, PTT) as measured at the screening visit
- Use of lipid-lowering medications or medications known to alter lipoprotein metabolism (fibrates, niacin, sex hormones, hormonal replacement therapy, etc.). *
- Any major acute or chronic diseases that may interfere with the study outcomes
- Gastrointestinal diseases affecting absorption including gastric bypass, ulcerative colitis, Crohn's disease, or chronic diarrhea
- unwillingness to adhere to study protocol
- non-English speaking
- no Social Security number

* If, however, interruption of lipid lowering medication is deemed safe and his/her primary care physician agrees to taking off the potential study subject from the lipid-lowering medication, such subject may be enrolled into the study after a 4-week washout phase.

c) Withdrawal/Termination criteria: low compliance, defined as taking less than 80% of study capsules, or inability to comply with the study schedule. Also subjects may not participate in another study while participating in this study.

D. **Risk/benefit assessment:** No major risks or hazards are expected.

1. **Physical risk:** No known risks are associated with the ingestion of EPA or DHA capsules. In subjects with prolonged coagulation time, there may be a risk of further increase in coagulation time. Therefore, subjects will be screened for coagulation

problems before enrollment into the study, specifically during the preadmission screening visit.

Blood draw: There is a small amount of bruising and discomfort, and rarely infection, associated with the drawing of blood samples. Every effort will be made to minimize discomfort to volunteers.

There is small risk of bleeding associated with the injection of heparin (50 IU/kg body weight) which is performed for the measurement of lipoprotein lipase and hepatic lipase.

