2. **Study Procedures:** Study subjects will be recruited as described below. Selection for a screening visit will occur via telephone interviews. Selected subjects will then report to

the MRU for the screening visit 1, after a 12-hour fast, for the measurement of plasma lipid, CRP, and glucose levels, and for the assessment of blood pressure and abdominal adiposity. Subjects that meet the inclusion criteria for the study based on screening visit 1 results will be invited for a second screening visit following a 12-hour. During screening visit 2, blood will be drawn for CBC, chemistries, lipid profile, TSH and PT/PTT. The subjects meeting all the inclusion and exclusion criteria will be enrolled into the study at visit 0 (enrollment visit). At visit 0 subjects will sign the Informed Consent Form and meet with the study dietician who will provide instructions on how to follow a Therapeutic Lifestyle Changes diet (25-35% of calories as total fat, <7% as saturated fat, and <200 mg/day cholesterol) throughout the study.

The table below illustrates the measurements to be performed at each study visit after enrollment into the study. At the screening visit, subjects will undergo medical history, weight and waist circumference measurement, blood pressure and vital signs assessment, and a blood draw for the assessment of clinical chemistry profile and hs-CRP.

At visit 0, subjects will receive the supply of supplements for Phase 1 of the study, at visit 2 they will receive the Phase 2 study supplements, at visit 4 they will receive the Phase 3 study supplements and at visit 5 will receive the Phase 4 study supplements.

Outpatient visit	Measurement	ml of blood
Phase 1, visit 1	Weight, waist circumference, blood pressure, vital signs Clinical chemistries, hs-CRP, plasma cytokines and lipids Blood monocyte isolation and response to LPS.	120
Phase 1, visit 2	Weight, waist circumference, blood pressure, vital signs Dietary counseling and supplement distribution Plasma cytokines and lipids, enzyme (CETP, HL, LPL, LCAT) concentration and activity	40
Phase 2, visit 3	Weight, waist circumference, blood pressure, vital signs Clinical chemistries, hs-CRP, plasma cytokines and lipids Blood monocyte isolation and response to LPS.	120
Phase 2, visit 4	Weight, waist circumference, blood pressure, vital signs Supplement distribution Plasma cytokines and lipids, enzyme (CETP, HL, LPL, LCAT) concentration and activity	40

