1. **Recruitment:** Participants will be recruited from the Greater Boston area using several recruitment strategies such as advertisements in newspapers, local newsletters and flyers posted on university websites (Tufts University, Boston University). Additionally, the Metabolic Research Unit (MRU) resources include a roster of >20,000 names of subjects from which potentially qualifying women and men can be identified and contacted through the use of direct mailings. Although employees will not be targeted for recruitment and enrollment, employees of Tufts University and/or the HNRCA (employee-subjects) who voluntarily want to participate in the study will be eligible for screening and enrollment. In order to qualify for the study, employee-subjects must respond to IRB-approval advertisement of their own accord and will not be directly approached by any person seeking to recruit them for participation in the study. Members of the research team, as direct-report subordinates of the PI and anyone who is direct-report subordinate to any of the research team members in any other capacity will not be eligible to participate in the study. If employee-subjects qualify to participate in the study, they cannot participate as volunteers during hours in which they are being compensated by Tufts University for their regular work. This includes use of vacation, personal days and sick time.
2. **Registration:** This study will be registered on clinicaltrials.com.
3. **Screening Interview/questionnaire:**
 - Prescreening*

After potential volunteers have been identified they will complete a 20 minute telephone interview (Prescreening Phone Questionnaire). The interviewer will explain the study design and ask questions to assess whether a potential volunteer meets the inclusion criteria.
 - Screening*

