If, on the basis of the prescreening questionnaire, the interviewer determines that the potential volunteer meets the study inclusion criteria, s/he will be asked to attend Screening visit 1 in the fasted state (12 hrs) to determine study eligibility. During that visit potential volunteers will have blood pressure, height and body weight recorded, BMI calculated, 5 ml (1 teaspoon) of blood drawn, and a medical history administered by a nurse. A Registered Dietitian will obtain information on the potential volunteer's dietary habits with specific emphasis on the habitual consumption of fish. If eligible based on results of screening visit 1, subjects will be asked to return to the MRU for screening visit 2 for a 21.5 mL blood draw (4.3 teaspoons).
4. **Transportation:** The volunteers will be expected to provide their own transportation to the facility. The facility is accessible by public transportation. Additionally, volunteers who choose to drive to the HNRC can obtain parking validation at a reduced rate.
5. **Informed consent process and timing of obtaining of consent:** Nursing staff or the Principal Investigator will administer both the Screening Informed Consent Form as well as the Study Informed Consent Form from each potential volunteer. The consent interview will be administered by the Principal Investigator in a private room in the MRU at the HNRCA. The Screening Informed Consent Form will be obtained on the day of the volunteers screening visit. Subjects will be given the time each of them requests to consider participation in the study. The Study Informed Consent Form will be obtained from each volunteer on the first day of the study after they have had the purpose of the study explained to them and given the opportunity to read the form and ask questions. Before consent, each potential subject will be asked to describe the study back to the investigator to make sure he/she has a good understanding of the purpose of the study and the level of commitment required. After all the questions have been answered, and the volunteer fully understands the study procedures, the nursing staff or study coordinator will obtain the signed informed consent from the volunteer. The volunteers

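### A lipid-lowering drug may be stopped for the trial about 4 weeks before study consent is signed, and the risk section omits an interruption implied to last about 38 weeks

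*Combined protocol and SAP*

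**What the plan says.** Section C.1.b lists as an exclusion "Use of lipid-lowering medications or medications known to alter lipoprotein metabolism". Its footnote relaxes this where "interruption of lipid lowering medication is deemed safe and his/her primary care physician agrees to taking off the potential study subject" from the drug; then "such subject may be enrolled into the study after a 4-week washout phase". It does not say who judges safety, how long the drug stays off, or when it may be restarted.

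On consent, E.2 places enrolment at visit 0 and adds: "At visit 0 subjects will sign the Informed Consent Form". G.5 agrees: "The Study Informed Consent Form will be obtained from each volunteer on the first day of the study". G.5 also describes explaining the study's purpose, giving time to read the form and ask questions, and a check of understanding in which "each potential subject will be asked to describe the study back to the investigator to make sure he/she has a good understanding".

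Two steps come earlier. At the telephone prescreen (G.3), "The interviewer will explain the study design". Then, under G.5, "The Screening Informed Consent Form will be obtained on the day of the volunteers screening visit".

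Section D expects no major risk. It discusses the capsules and coagulation, blood drawing, heparin and confidentiality. Stopping lipid-lowering treatment is not among them.

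**The concern.** Someone may give up a prescribed drug in order to qualify for the trial before signing the study consent and, on the natural reading of G.5, before showing that they understand the study. For these people the drug stop is arguably the weightiest part of taking part, yet the consent process comes after it.

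The risk section does not weigh the time without the drug either. The plan itself treats LDL as atherogenic (section II.A), assumes in section B that DHA raises LDL-C, and expects no direct benefit to volunteers (D.5). What is at stake is informed choice and a complete risk statement. The estimand, analysis and power are untouched.

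**Working it through.** **Order of events**

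1. The footnote to C.1.b places a 4-week washout before enrolment.
2. E.2 places enrolment at visit 0, and the study consent is signed at that visit. G.5 gives the first day of the study, which is consistent.
3. The 4-week placebo lead-in cannot be this washout. Lead-in capsules are handed out at visit 0 (E.2), when the washout is already over.
4. The drug stop therefore precedes study consent by at least about 4 weeks, wherever the washout falls relative to the screening visits.

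**Length of the interruption**

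Inputs: washout 4 weeks (C.1.b footnote); phases of 4, 10, 10 and 10 weeks (E.3); breaks between phases usually under 3 weeks (section A).

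- Study length: 4 + 10 + 10 + 10 = 34 weeks, which reproduces the plan's figure.
- Off-drug time without breaks: 4 + 34 = 38 weeks.
- Share before study consent: 4/38 = 10.5%.
- Share on DHA: 10/38 = 26.3%.
- Upper case, assuming a 3-week break at each of the three phase transitions: 3 × 3 = 9, and 38 + 9 = 47 weeks.

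**Lipid monitoring while off the drug**

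Plasma lipids appear at all 7 study visits in the E.2 table. The visits are grouped at the ends of the phases:

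| Phase end | Weeks off drug |
|---|---|
| Lead-in | 4 + 4 = 8 |
| First supplement | 8 + 10 = 18 |
| Placebo washout | 18 + 10 = 28 |
| Second supplement | 28 + 10 = 38 |

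Lead-in samples are taken in the last week of that phase (E.1). The first study-visit lipid value therefore comes 4 + (3 to 4) = 7 to 8 weeks after the stop, and later ones are about 10 weeks apart. A screening lipid value may come sooner, depending on when the drug is stopped.

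**The case against.** The strongest objection is that consent is in two stages and the screening form cannot be seen. If the drug is stopped after the first screening visit, the person has already signed something, and that form may cover the stop. This is fair, and it rules out any claim that there is no consent at all. But no protocol text requires the screening form to cover the stop or to come before it.

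The describe-back sentence in G.5 does not name a form. Its position after the study-consent sentence favours the reading used here but does not prove it. The explanation could also be given well before signing. Neither point moves the study signature itself.

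The 38 weeks is an inference. Drug use is only an entry exclusion; restarting is not among the withdrawal criteria in C.1.c, and nothing forbids it. Staying off is the natural reading because lipids are measured in every phase, but the durations and percentages assume no restart. The 4-week gap before consent does not depend on that.

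Real safeguards exist:

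- a judgement that stopping is safe, and the physician's agreement;
- diet counselling;
- lipids at every study visit;
- four-weekly calls, made for adherence;
- adverse-event reporting and IRB review;
- freedom to withdraw at any time.

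They reduce the clinical risk. However, the study visits and calls begin only after enrolment, and a physician's agreement is not the participant's own study consent.

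Finally, a lighter remedy is possible: require the screening consent to cover and precede the stop. That would close part of the gap, and it avoids signing full consent with people who later fail screening. It would match the preferred fix only if it carried the same explanation and check of understanding.

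**Conclusion.** The concern holds. The stated order places a trial-driven drug stop at least about 4 weeks before study consent, and section D does not mention the interruption. The implied off-drug time is about 38 weeks, or up to about 47 with the assumed breaks.

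The conclusion on timing rests only on the footnote, E.2 and G.5. The duration also assumes that the drug is not restarted during the study. The consent forms are not available, so the point about the missing risk is limited to section D. Severity is minor to moderate: no result changes, and the number of subjects affected is not given. It should still be fixed, because the protection is owed to each person who uses the exception.

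**What to change.** For anyone who would stop a lipid-lowering drug for the trial:

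1. Amend the C.1.b footnote, E.2 and G.5 so that the Study Informed Consent, including the describe-back step, is completed before the drug is stopped.
2. State the expected off-drug time (about 38 weeks, longer with breaks) and its risk in section D, in the consent form and in the request to the primary care physician.

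The cost is one protocol and consent amendment, with no added assay and no change to endpoints or sample size. A few people may decline once they see the off-drug time, and some who sign early may fail a later screening test. An extra contact is needed only if the drug would be stopped before the first screening visit.

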B: Rationale: In vitro and in vivo (both human and animal) studies suggest differential effects of EPA and DHA (16). This study represents the first systematic effort to characterize the differential effects of EPA and DHA on inflammation and lipid metabolism in humans. The central hypothesis of this proposal is that EPA and DHA, in addition to common effects, have distinct and separate effects on systemic inflammation and lipid metabolism. The objective of the proposed study is to provide critical information regarding both common and distinctive roles of EPA and DHA in systemic inflammation and lipid metabolism. The current gaps in knowledge on the differential effects of EPA and DHA undermine the ability to provide optimal guidance for the use of EPA or DHA in specific conditions and in population-wide recommendations aimed at improving public health. Efforts in understanding the distinctive effects of EPA and DHA on inflammation and lipoprotein metabolism can have remarkable implications for the prevention and treatment of inflammatory states, cardiovascular disease, dyslipidemia, and other disorders, and ultimately lead to healthcare cost savings and improvement in quality of life.

A. Experimental design: randomized, placebo-controlled, double-blind, cross-over study (Figure 1). Subjects will be randomized to one of two sequences of supplementation [EPA followed by DHA (n=12), or DHA followed by EPA (n=12)] using a computer-generated randomization schedule. To reduce patient scheduling issues and increase compliance, subjects enrolled in to the study will be allowed short breaks (usually less than 3 weeks) between phases. EPA and DHA capsules will be identical and will be provided in a blind fashion by the manufacturer (Prevention Pharmaceuticals). The study physician will be the only member of the research team with knowledge of the supplement assignment. Code will be broken at the end of the study.

[figure not shown]

Figure 1. Study design.

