One risk is the possible loss of confidentiality. Stored samples will be labeled with a unique number (code) that will not contain any private information such as name or date of birth to ensure the samples cannot be identified. There is no intention for allowing anyone other than the principal investigator to have access to these codes. If [name] turns this study over to a new principal investigator, she will give the key code to the new principal investigator. Every possible precaution will be taken to keep volunteer information confidential. However, despite strict measures, possible loss of confidentiality remains as a risk of participation in this research study.

2. **Psychological risk:** No psychological risks are expected

3. **Social risk:** No social risks are expected

4. **Economic risk:** No economic risks are expected

5. **Benefit of participating in the study:**

There will be no direct benefits to the volunteer for study participation. There is a possibility of benefit from reduction in inflammation and TG levels during the active treatment phases of the study. Knowledge may be gained by their participation, which may benefit the health of others.

E. **Specific methods and techniques used throughout the study:**

1. **Laboratory tests:**

During the last week of the placebo/lead-in phase and each of the two supplementation phases a total of 160 ml of blood (32.5 teaspoons) will be drawn (120 ml [24.4 teaspoons] in visit 1 and 40 ml [8.1 teaspoons] in visit 2). The following will be measured:

- Clinical Chemistry Profile (glucose, albumin, ALP, SGPT, SGOT, blood urea nitrogen, creatine phosphokinase, creatinine, lactate dehydrogenase, total protein, bilirubin, globulin, albumin/globulin ratio, uric acid, calcium, phosphorus, magnesium, sodium, potassium, chloride, total and LDL-cholesterol, triglyceride)
- PT/PTT
- CRP; immunoassay
- Plasma cytokines (TNF- α , IL-6, and MCP-1); multiplex immunoassay
- Monocyte isolation and response to LPS: cell culture
- Monocyte transcriptomics: GeneChip® Human Genome U133 Plus 2.0 Array (Affimetrix) and real time PCR
- Monocyte lysates: AMPK phosphorylation, TAK1 phosphorylation, NF-kB by Western blotting
- Plasma lipid (TC, TG, LDL-C, HDL-C): automated assays
- Enzyme concentration (CETP, LCAT, LPL and HL): ELISA
- CETP, LPL and HL activity: enzymatic release of ¹³C labeled fatty acids, assessed by liquid scintillation counter

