EPA and DHA capsules will be manufactured by Prevention Pharmaceuticals through fish oil extracting procedures from farmed sardines and will be delivered to the Principal Investigator in a blinded fashion (marked A and B, the investigator will not know the content of these). Placebo capsules will be prepared by Prevention Pharmaceuticals using high-oleic acid sunflower oil (commercially available from J Edwards International) and will be delivered to the Principal Investigator marked as C (PI will know the identity of placebo capsules to allow their administration in the lead-in and washout phases). Capsules will be stored in the Principal Investigator Office, in a locked cabinet. Capsules will be stored at room temperature and instructions will be provided to subjects both orally, at the time of supplement distribution to study subjects, and in writing on the supplement bottle label.

3. **Subject Timeline:** The study is approximately 34-week long and includes a 4-week placebo lead-in phase, followed by a 10-week EPA or DHA supplementation phase, a 10-week placebo/washout phase and then a cross-over to a 10-week DHA or EPA supplementation phase. The length of the study may be longer if a participant takes a break between phases. A detailed description of the schedule of vital sign assessments, blood draws, and other study procedures is provided in Table 1. Subjects will be allowed to change the schedule of their visits by 5 days (before or after the scheduled appointment) to allow for unexpected events (weather, illness, etc.).

F. Assessment of Subject Safety and Development of a Data and Safety Monitoring Plan

1. Definition of Serious Adverse Event (SAE) and Adverse Event (AE) for this study:

An **Adverse Event (AE)** is defined as any untoward or unfavorable medical occurrence in a human subject, including any abnormal physical exam or laboratory finding, symptom, or disease, temporally associated with a subject's participation in the research.

A **Serious Adverse Event (SAE)** is any Adverse Event (AE) that:

1. Results in death, or
2. Is life-threatening, or
3. Results in hospitalization or prolongation of existing hospitalization, or
4. Results in a persistent or significant disability/incapacitation, or
5. Results in a congenital anomaly/birth defect, or
6. May jeopardize the subject's health and may require medical or surgical intervention to prevent one of the other outcomes listed above.

2. Reporting timeframe for SAEs and AEs:

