9. **Procedures to protect subject confidentiality:** The identity of the volunteers, medical records and data relating to this research will be kept confidential, except as required by law and except for inspections by the USDA or the Tufts Medical Center Institutional Review Board. The medical records will be filed in the medical record room only available to designated research staff. Upon entry into the research study, the volunteer will be assigned a unique code number. For storage, blood samples will be identified with this unique code number (not related to medical record number), date, laboratory generated login number and sample description (i.e. plasma, serum).

10. **Confidentiality:**

- a. **Certificate of Confidentiality:** None

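### Stored samples carry a fixed subject code and the date, and placebo is always phases 1 and 3, so assay staff could infer placebo versus active, and the plan states no safeguard

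*Combined protocol and SAP*

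**What the plan says.** **Label.** Section G.9 sets the rule for stored material: "blood samples will be identified with this unique code number (not related to medical record number), date, laboratory generated login number and sample description". The confidentiality paragraph for employee-subjects under G.10 repeats the rule: "date, laboratory generated login number and sample description (i.e. plasma, serum). All samples and data generated from the research study will be labeled". Both give plasma and serum as the sample descriptions. G.10.b adds a general rule: "All samples and data generated from the research study will be labeled and/or recorded with a unique code number and no other identifier".

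**Phase order.** Section E.3 says that the study "includes a 4-week placebo lead-in phase, followed by a 10-week EPA or DHA supplementation phase, a 10-week placebo/washout phase", with the second active phase last. The Experimental design section randomizes only which active oil comes first.

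**Blinding.** The Experimental design section calls the trial double-blind and says: "The study physician will be the only member of the research team with knowledge of the supplement assignment". Section E.2 marks the two active oils A and B, with their content hidden from the principal investigator. It marks placebo C and says that the principal investigator will know which capsules these are.

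**Laboratory.** Section G.10.c limits laboratory personnel to de-identified data. Section E.1 lists automated lipid assays, multiplex immunoassay for cytokines, ELISA, cell culture, arrays, real-time PCR, and "Monocyte lysates: AMPK phosphorylation, TAK1 phosphorylation, NF-kB by Western blotting". No section mentions masking to visit or phase, assay order, or a rule for repeating or rejecting a value.

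**Aims.** Aims 1 and 2 each compare EPA and DHA with placebo as well as with one another.

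**The concern.** A code that stays the same for a subject throughout, together with a date, puts that subject's tubes in time order. Because placebo holds the same two positions for everyone, time order is also treatment status. De-identification does not help here: it hides who the subject is, not which phase the tube came from.

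What is at stake is the measurement of the placebo contrasts. They have little other protection. Placebo's position is not randomized, and the principal investigator knows the placebo capsules by design. Masked measurement is the main protection left. It matters most where an operator's handling or judgement enters the result: Western blots, PCR and array handling, and the choice to repeat or discard a value.

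**Working it through.** No published figure is in dispute, so the check is whether code plus date separates placebo from active, for which assays, and for how many sample sets.

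**Inputs**
- Label content: G.9 and the employee-subject paragraph.
- Phase order: E.3. Randomized element: Experimental design.
- Visits by phase, from the table in E.2: phase 1 has visits 1 and 2, phase 2 has visits 3 and 4, phase 3 has visit 5, and phase 4 has visits 6 and 7.
- Completers: 24, from Sample size and statistical analyses.

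**Step 1: which contrast the 24 belongs to.** The plan describes a 2x2 cross-over with ratio 0.79, CV 0.28, 80% power and two-sided 0.05. Take 0.79 as the ratio between the two active phases and 0.28 as a within-subject CV.
- Within-subject SD on the log scale: √ln(1 + 0.28²) = 0.275.
- Standard error: 0.275 × √(2/24) = 0.0793.
- |ln 0.79| / 0.0793 = 0.2357 / 0.0793 = 2.97.
- With 22 degrees of freedom, the noncentral t gives 81.1% power, and 24 is the smallest even number reaching 80%.

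On this reading the plan's figure is reproduced, and placebo does not enter it. Nothing below changes it.

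**Step 2: date order mapped to treatment** (P = placebo, A = active)

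| Measurement | Visits | Sequence EPA–DHA | Sequence DHA–EPA |
|---|---|---|---|
| Cytokines, lipids | 1–7 | P P A A P A A | P P A A P A A |
| Monocytes, hs-CRP | 1, 3, 6 | P A A | P A A |
| Enzymes | 2, 4, 7 | P A A | P A A |

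The pattern is the same under both sequences. Date order therefore separates placebo from active in a complete set and says nothing about EPA versus DHA. In the three-visit sets the earliest tube is the placebo tube.

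**Step 3: do breaks or visit windows hide the order?** No. Breaks between phases (Experimental design) and the 5-day scheduling allowance (E.3) alter the spacing, not the order.

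**Step 4: what must staff have?** They need the subject's other dates, or the start date, and the schedule. The fixed code links the tubes, and the schedule is common to all subjects. One tube's calendar date alone does not show its phase.

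**Step 5: sample sets where handling matters most.** Monocytes are isolated at visits 1, 3 and 6. With 24 completers that is 3 × 24 = 72 sets: 1 × 24 = 24 placebo and 2 × 24 = 48 active. That lysates and RNA come from these isolations, and carry the G.9 label, is an assumption. The documents do not say how those aliquots are labelled.

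**The case against.** **The label is for storage, and it also carries a laboratory login number.** Staff may work from that number alone. This stands as far as it goes: bench procedure is not described. A reader might infer that the placebo contrasts are not measured blind, or that every tube can be recognised on sight. The documents support neither. They show that phase could be inferred, and that nothing stated prevents it. The plan also does not say whether the login number is non-sequential. A sequential one would carry the same order.

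**The label rule names plasma and serum, whose assays are largely instrument-read.** This stands. Automated lipids, multiplex cytokines and ELISA leave little room for reading bias, though that is a judgement and not a statement in the plan. The larger worry, the monocyte work, depends on those aliquots being labelled in the same way.

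**The date label may seem to contradict "labeled and/or recorded with a unique code number and no other identifier" in G.10.b.** A reader might call this an inconsistency. It is a weak one: those paragraphs concern confidentiality, an identifier there means something that names the person, and the employee-subject paragraph sets the two rules side by side.

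**Placebo is open to the principal investigator anyway.** True, and the statement that only the study physician knows the assignment is best read as covering the randomized EPA/DHA order. Masking the bench will not make the placebo contrast randomized. It removes one avoidable source of bias from a contrast that both aims name.

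**Conclusion.** The point holds in a limited form. The stated label exposes phase order to anyone who has a subject's date series and the schedule, and the plan gives no safeguard for blinded measurement of the placebo contrasts. The randomized EPA-versus-DHA comparison is untouched, and no sample-size figure changes.

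The main exposure is 72 monocyte sample sets (24 placebo, 48 active), on the assumptions that 24 subjects complete and that lysates and RNA carry the same label. Decisions to repeat or drop values are exposed for any assay.

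The size of any bias cannot be derived from the documents. It is tempting to set a guessed reading shift against the TNF-alpha ratio of 0.79. That would take a shift from operator-read assays and divide it by an effect measured by immunoassay and used to size the EPA/DHA cross-over, which the label does not unmask. Nor do the documents show that any bias would always favour the active oils, plausible though that direction is. This is a low-cost improvement to the plan, not a defect in its main comparison.

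**What to change.** Amend G.9 and the employee-subject paragraph, and add a sentence to E.1, to the following effect:

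- Stored aliquots, including lysates and RNA, are assayed under a non-sequential accession or login number and sample type only.
- All of a subject's samples are run in one batch, in random order.
- The key linking that number to subject code, date and visit is held off the bench in REDCap. It is released when results and decisions to repeat or reject values are final.

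REDCap and a data-management core are already in place under G.10.b.

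**Cost.** Protocol wording, a look-up step, and batch lists drawn up by someone away from the bench. No visit, blood volume or sample size changes.

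**What it does not mend.** Fresh monocyte culture on the visit day cannot be masked this way. The placebo contrast stays non-randomized, with placebo known to the principal investigator, and the report should say so.
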